2.4. Endpoints for the Expansion

Primary Endpoint

- CR rate for MDS patients ([Appendix 2](#)) and AML patients ([Appendix 11](#)).

Secondary Endpoints

- OS;
- For MDS cohort: disease-specific efficacy measures, such as marrow CR (mCR), Partial Remission (PR), Stable Disease (SD), Partial or Complete Cytogenetic Response, and Hematologic Improvement (HI) ([Appendix 2](#));
- For AML cohort: disease-specific efficacy measures, such as CR with Incomplete Hematologic Recovery (CRi), Complete Remission with partial hematologic recovery (CRh), Morphologic Leukemia-Free State (MLFS), PR, and SD ([Appendix 11](#));
- Duration of CR;
- Time to CR;

- Adverse events and laboratory abnormalities as graded by NCI CTCAE v.4.03;
- Pharmacokinetics parameters of glasdegib;
- QTc interval.

CCI

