Appendix 11. 2017 ELN Response Criteria for Acute Myeloid Leukemia

Response Criteria	Neutrophils (μL)	Platelets (μL)	Bone Marrow Blasts (%)	Other
Complete Remission without Minimal Residual Disease (CR_{M RD})				If studied pretreatment, CR with negativity for a genetic marker by RT qPCR, or CR with negativity by multiparameter flow cytometry
Morphologic Complete Response (CR)	$\geq 1,000$	$\geq 100,000$	<5; no peripheral blasts; no blasts with Auer rods	No EMD; Transfusion independent
Complete Remission with partial hematologic recovery (CRh)¹	>500	>50,000	<5; no peripheral blasts; no blasts with Auer rods	No EMD; Not qualifying for CR
Morphologic CR with incomplete blood count recovery (CRi)	<1,000 -or-	<100,000	<5; no peripheral blasts; no blasts with Auer rods	No EMD; Either neutrophils or platelets not recovered; Not qualifying for CRh
Morphologic leukemia-free state (MLFS)	<1,000 -and-	<100,000	<5; no blasts with Auer rods	No EMD; Neutrophils and platelets not recovered; BM not merely “aplastic”; BM cellularity must be 10%, or 200 cells enumerated; Not qualifying for CRi
Partial remission (PR)	$\geq 1,000$	$\geq 100,000$	blasts decrease to 5-25 and $\geq 50\%$ decrease from pretreatment	Blasts $\leq 5\%$ if Auer rod positive
Stable Disease (SD)				Absence of CR _{M RD} , CR, CRh, CRi, PR, MLFS and criteria for PD not met. Should last at least 3 months.

Progressive Disease (PD)			>50% increase in blasts from pretreatment (if baseline is <30% blasts, must have at least 15% increase; or >70% blasts for ≥3 months; no improvement in ANC (>0.5 x 10 ⁹ /L [500 μL], and/or platelet count to >50 x 10 ⁹ /L [50 000 μL nontransfused]); or > 50% increase in peripheral blasts (WBC count x % blasts) to >25 x 10 ⁹ /L (25000 μL); or new EMD
Relapse			
Hematologic relapse (after CRMRD-, CR, CRi)			Bone marrow blasts >5%; or Reappearance of blasts in the blood; or Development of EMD
Molecular Relapse (after CRMRD-)			If studied pretreatment, reoccurrence of MRD as assessed by RT-qPCR or multiparameter flow cytometry
Treatment Failure			
Primary refractory disease	For Non Intensive: Treatment Failure is defined as failure to achieve CR or CRh following up to 6 cycles of study treatment.		
Death in aplasia	Deaths occurring ≥7 days following completion of initial treatment while cytopenic; with an aplastic or hypoplastic bone marrow obtained within 7 days of death, without evidence of persistent leukemia.		

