7.2. Efficacy Analysis

For primary and secondary efficacy analyses, no values will be imputed for missing data. Censoring for time-to-event endpoints are defined in [Section 6.1](#). In the assessment of response (at interim or final analysis), patients who are not known to have achieved response will be counted as non-responders.

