8.2.2.2.2. Other Efficacy Measures

Specifically, for AML cohort, the following binary efficacy endpoints (with 95% exact CI) will be summarized in frequency tables, proportion of patients achieving CR, CRh, CRi, CR/CRi, MLFS, PR, SD, CRc, , CRm, and CR+PR.

For MDS cohort, the following binary efficacy endpoints (with 95% exact CI) will be summarized in frequency tables, proportion of patients achieving CR, marrow CR, PR, SD, CR+PR, and Partial or Complete Cytogenetic Response, as well as the proportion of patients ever achieving HI.

The FAS will be used.

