Appendix 4. 2017 ELN Response Criteria for Acute Myeloid Leukemia

Response Criteria	Neutrophils (μL)	Platelets (μL)	Bone Marrow Blasts (%)	Other
Complete Remission without Minimal Residual Disease (CR_{MRD})				Assessed in CR and CRi patients only by central multiparameter flow cytometry
Morphologic Complete Response (CR)	$\geq 1,000$	$\geq 100,000$	<5 with spicules; no peripheral blasts, no blasts with Auer rods	Transfusion independent, no EMD
Complete Remission with partial hematologic recovery (CRh)¹	>500	>50,000 □	<5; no peripheral blasts; no blasts with Auer rods	No EMD; Not qualifying for CR
Morphologic CR with incomplete blood count recovery (CRi)	<1,000 -or-	<100,000	<5	Either neutrophils or platelets not recovered, no EMD
Morphologic leukemia-free state (MLFS)	<1,000 -and-	<100,000	<5 with spicules and no blasts with Auer rods	Neutrophils and platelets not recovered, Flow cytometry negative, no EMD
Partial remission (PR)	$\geq 1,000$	$\geq 100,000$	decrease to 5-25 blasts and $\geq 50\%$ decrease from pretreatment	Blasts $\leq 5\%$ if Auer rod positive
Stable Disease (SD)				Absence of CR _{MRD} , CR, CRi, PR, MLFS and criteria for PD not met. Should last at least 3 months.

Progressive Disease (PD)
			
>50% increase in blasts from pretreatment (if baseline is <30% blasts, must have at least 15% increase; or >70% blasts for ≥3 months; no improvement in ANC (>0.5 x 10⁹/L [500 μL], and/or platelet count to >50 x 10⁹/L [50 000 μL nontransfused]; or > 50% increase in peripheral blasts (WBC count x % blasts) to >25 x 10⁹/L (25000 μL); or new EMD
	
--	--	--	--	--

ANC=Absolute neutrophil count; WBC=white blood cell; EMD=extramedullary disease.

There is no minimum requirement for bone marrow cellularity or hemoglobin concentration for response criteria.

Composite from Cheson, BD, Bennett JM, Kopecky KJ, et al. Revised recommendations of the International Working group for diagnosis, standardization of response criteria, treatment on outcomes and reporting standards for therapeutic trials in acute myeloid leukemia. J Clin Oncol 2003; 21(24):4642-4649 and Döhner H, Estey E, Grimwade D, et al. Diagnosis and management of AML in adults: 2017 ELN recommendations from an international expert panel. Blood 2017;129(4): 424-47.²

¹CRh is not part of the 2017 ELN recommendations, but is a required assessment for this study.

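### SAP Appendix 4 and protocol Appendix 11 define the AML secondary endpoint MLFS differently, and the SAP names no source for the flow cytometry result that its own definition requires

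*SAP*

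**What the plan says.** Protocol section 2.4 lists MLFS among the disease-specific secondary measures of the AML expansion cohort ("Morphologic Leukemia-Free State (MLFS), PR, and SD"). SAP 8.2.2.2.2 reports it as a proportion with an exact 95% CI on the full analysis set, in the series "CR, CRh, CRi, CR/CRi, MLFS, PR, SD".

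The SAP's MLFS row in Appendix 4 requires both neutrophils and platelets to be unrecovered, marrow blasts below 5% with spicules and no Auer rods, and ends "platelets not recovered, Flow cytometry negative, no EMD". Flow cytometry appears in one other row of that appendix, complete remission without minimal residual disease: "Assessed in CR and CRi patients only by central multiparameter flow cytometry".

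The MLFS row of protocol Appendix 11 has no flow condition and no spicule condition. It excludes a marrow that is merely aplastic and ends "BM cellularity must be 10%, or 200 cells enumerated; Not qualifying for CRi". That appendix uses flow negativity to define a response only for remission without residual disease, "CR with negativity by multiparameter flow cytometry"; flow also appears there in the definition of molecular relapse.

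SAP 7.2 sets the default for an unknown response: "patients who are not known to have achieved response will be counted as non-responders".

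**The concern.** Two definitions of one reported endpoint are in force, and SAP section 1, which lists the changes made after Amendments 5 and 6, mentions no change to MLFS. Protocol section 9 lets the SAP modify the protocol's plans and asks for an amendment only for major changes to the primary endpoint. An unflagged SAP definition of a secondary endpoint could therefore govern the analysis.

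The added flow condition matters most. A patient with both counts low and a cleared marrow is the intended MLFS case, yet the one flow assay the SAP describes is tied to CR and CRi patients. Without a result, such a patient is scored as not achieving MLFS. Because the SD row requires the absence of MLFS, the patient can then be counted as SD if that state lasts at least 3 months. Two programmers, each working from one document, could report different MLFS, CRi and SD counts from the same patients.

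**Working it through.** The plan states no figure for MLFS, so there is none to reproduce. The check compares the two definitions and then follows a patient through the SAP's rules.

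**1. Conditions for MLFS, side by side**

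| Condition | SAP Appendix 4 | Protocol Appendix 11 |
|---|---|---|
| Neutrophils <1,000 and platelets <100,000 | yes | yes |
| Marrow blasts <5%, no Auer rods, no EMD | yes | yes |
| Spicules | required | not stated |
| Flow cytometry negative | required | not stated |
| Marrow not merely aplastic | not stated | required |
| 10% cellularity or 200 cells enumerated | not stated | required |
| Does not qualify for CRi | not stated | required |

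The SAP adds two conditions and omits three.

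**2. Source of the flow result.** The MLFS row does not say whether the assay is central or local. The remission-without-residual-disease row covers CR and CRi patients. In the readable rows, protocol Table 3 (expansion) has aspirate/biopsy and genetics but no immunophenotyping, whereas Table 1 (lead-in) has an immunophenotyping row. As context, the Amendment 6 summary says immunophenotyping was removed because no study analysis required it. The biomarker rows and sections are redacted.

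**3. Does an MLFS patient fall in the CRi group?** The SAP's CRi row reads "Either neutrophils or platelets not recovered, no EMD", with blasts below 5% and no clause excluding other categories.

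- *Exactly one lineage unrecovered.* A patient with both counts low is not CRi and is outside the group for which the SAP describes flow.
- *Inclusive or.* Every patient who meets the SAP's MLFS row also meets its CRi row, since CRi then asks only for blasts below 5%, no EMD and a count not recovered. Flow would be available, but MLFS becomes a subset of CRi and counts in the reported CR/CRi rate. Nothing in the SAP separates the two.

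**4. Size under the first reading, if no flow result exists.** Take n = 30, the AML maximum in protocol 9.1.2. SAP 7.2 makes every such patient a non-achiever, so x = 0. The exact (Clopper-Pearson) limits are:

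- lower = 0
- upper = 1 − 0.025^(1/30) = 1 − exp(−3.6889/30) = 1 − 0.8843 = 0.116

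The report would show 0/30, 95% CI 0 to 11.6%, whatever the true number.

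The documents give no expected MLFS count, so the loss is shown over a range of assumptions. With k true MLFS patients, the estimate falls by k/30: 1/30 = 3.3, 3/30 = 10.0 and 5/30 = 16.7 percentage points. For the assumed k = 3, the protocol definition would give 10% (exact 95% CI 2.1 to 26.5%).

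**The case against.** A reader might infer that MLFS cannot be met as the SAP is written. The documents do not support that.

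- The word limiting flow to CR and CRi patients sits in the remission-without-residual-disease row. It says who is assessed for that category, and does not say that flow is done in no one else.
- The MLFS row does not ask for the central assay, so a local result would satisfy it.
- Protocol Table 3, footnote 16, requires an aspirate at every disease evaluation, for local staging and central biomarker work. What the redacted sections add is unknown.
- An inclusive or in the CRi row would bring these patients into the flow-tested group.

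All four stand. The contrast between or in the CRi row and and in the MLFS row favours exactly one lineage, but that is a reading.

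A reader might also infer that the SAP row admits an empty, aplastic marrow. That goes too far, because spicules are themselves a specimen-adequacy condition. What remains is that the protocol's explicit adequacy tests are missing from the SAP.

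Version lag may explain part of the mismatch. The SAP follows Amendment 6, and the Amendment 7 summary reports additions to protocol Appendix 11. That would explain the difference but would not reconcile it. The stakes are also limited: MLFS is one of several descriptive proportions, and SAP 4.1 states that there are no formal hypotheses.

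**Conclusion.** The conflict between the two definitions is certain from the readable text: two conditions added, three omitted, no change recorded. It is also certain that the readable SAP names no source for an MLFS patient's flow result, and that its default for an unknown response is non-achievement.

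The 0/30 result is conditional. It rests on 30 AML patients, no flow data in MLFS patients, and CRi meaning exactly one lineage unrecovered. If flow results exist, the reported rate can be above zero, but it would still be an MLFS rate under a definition other than the protocol's. If or is inclusive, the fault moves to an MLFS category that the SAP does not separate from CRi. The SAP row needs repair under either reading.

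The primary CR endpoint and the futility rule are not affected. The correction should be made before the AML analysis, as a matter of how a secondary endpoint is scored.

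**What to change.** Replace the MLFS row of SAP Appendix 4 with the protocol Appendix 11 row, including the clause that the patient does not qualify for CRi. Delete the flow condition and report flow status of MLFS patients descriptively where a result exists. If the sponsor does intend flow negativity as a criterion, the alternative is to name the assay, say who is tested, and state how a missing result is scored.

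Two further wording points belong with this:

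- State in the CRi row whether CRi means exactly one unrecovered lineage. The exclusion clause sends patients with both counts low to MLFS only under that reading.
- Reconcile the footnote to the AML response table in both documents, which says there is no minimum marrow cellularity for response criteria, with the 10% or 200-cell condition. Otherwise the copied row carries a contradiction with it.

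The cost is a few lines of SAP text and a footnote correction in both documents. No new sample, assay or visit is needed.
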